11.2. Appendix 2: Time & Events

11.2.1. Protocol Defined Time & Events

Protocol Activity ^{1,2}	Screening		Day 1	Treatment Period				Follow-up
	Week -4	Week -2		Day 15	Day 29	Un-scheduled	Early Withdrawal	Day 43 ± 3 ⁶
Informed Consent	X							
Entry Criteria	X		X					
Physical, Medical History, Demography	X							
HemoCue Hgb	X	X	X	X	X	X	X	
IVWRS Call	X	X	X	X	X	X	X	X
Females Only: Serum Pregnancy Test ³		X					X	X
Females Only: Estradiol and FSH (if required) ³		X						
ECG	X				X		X	
Vitals (Pre-dialysis and Post-dialysis) ⁴		X	X	X	X	X	X	X
Clinical Chemistry		X	X	X	X	X	X	X
Hematology		X	X	X	X	X	X	X
Folate and Vitamin B ₁₂	X							
Ferritin, transferrin, total iron, UIBC	X		X		X		X	X
Pharmacokinetic/Pharmacodynamic Samples			X	X	X		X ⁵	
Blood draw for PGx			X					
Adverse Events Assessment ⁷			X	X	X	X	X	X
Review Concomitant Medications	X		X	X	X	X	X	X

¹ All assessments should be done pre-dialysis except as noted.

² Allowable time window of ± 2 days for all study visits, except the follow-up visit for which it is ± 3 days.

³ As detailed in Inclusion Criteria in study protocol Section 5.2

⁴ Weight measured post-dialysis only & height measured at screening only.

⁵ Obtain samples as per the Day 29 visit in Table 2 of the study protocol. If subject does not receive a dose of study medication at this early withdrawal visit, no post-dose PK/PD samples should be obtained.

⁶ Subjects who withdraw early from treatment should attend a follow-up visit 14 days ± 3 days after the last dose of study treatment.

⁷ Serious adverse events are assessed from the time of consent as stated in study protocol Section 7.4.1.1

Pharmacokinetic/Pharmacodynamic Time and Events Table

PK/PD Sample	Day 1 (dose study med at clinic)	Day 15 (dose study med at home¹)	Day 29 (dose study med at clinic)
Plasma PK²	Pre-dose	1 st sample collected approx 6-10 hr post-dose on arrival. Additional sampling: 1, 2, and 3 h after this 1 st sample	Pre-dose, 1, 2, and 3 h post dose
EPO & VEGF²	Pre-dose	1 st sample collected approx 6-10 h post-dose on arrival. Additional sampling: 1, 2, and 3 h after this 1 st sample	Pre-dose and 3 h post dose
Hepcidin³	Pre-dose	Single sample during visit	Single sample during visit

¹ Subject to take their dose of study medication at home and arrive for clinic visit approx 6-10 h post-dose. Subjects may take their Day15 dose the evening prior to the Week 2 study visit to accommodate the 6-10 h PK/PD sampling window

² Sample to be collected within 30 minutes of planned collection time

³ Sample can be pre- or post-GSK1278863 administration

11.3. Appendix 3: Assessment Windows

11.3.1. Assessment Windows Assignment

For efficacy data, laboratory data, vital signs, and ECG measurements to be summarized or analyzed by visit, unscheduled and early withdrawal (EW) data measurements will be assigned to one of the protocol specified visits using the following algorithm:

1. Determine Study Day of assessment (refer to Section 11.6.1)
2. Based on the Study Day, assessment will be assigned as shown in Table 10 below

Table 10 Assessment Windows

Study Day of Assessment	Assessment Window	Target Study Day of Window
1	Day 1	1
2 to 22	Day 15	15
23 to 36	Day 29	29
This will not be slotted	Day 43 (Follow-up)	

Note: If an unscheduled value is recorded prior to Day 1 then this will be slotted as follows (Table 11; Refer to Section 11.5.2 for the derivation of Baseline):

Table 11 Assessment Windows for Screening

Study Day of Assessment	Assessment Window
<= -22	Week -4
-21 to -1	Week -2

As specified in the protocol, if a subject does not receive a dose of study medication at the early withdrawal visit, no post-dose PK/PD samples should be obtained. Hence if we do have EW EPO, hepcidin and VEGF values, it will be slotted to the appropriate visit as specified in Table 10 and summarized. These parameters are collected at scheduled time points (e.g. 6 to 10 hrs post-dose) within a visit and so this data will be reported as pre-specified for the tables and by actual time for graphics.

Local laboratory assessments (efficacy or safety) will not be slotted and will not be summarized. Only central lab assessments will be summarized. For parameters which are not scheduled to be assessed at particular visits, the all-inclusive windows defined in Table 10 and Table 11 above will still be used. However, if a value is slotted to a visit unscheduled for a parameter, it will not be summarized but will be included in data listings. Assessments at unscheduled visits will be included for ‘any time on-treatment’ time points and ‘any time post-treatment’, and in data listings, as well any algorithms that make use of additional data.

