5.6. Withdrawal/Stopping Criteria

A subject may withdraw from study treatment at any time at his/her own request, or may be withdrawn at any time at the discretion of the investigator for safety, behavioral or administrative reasons. If a subject withdraws from the study, he/she may request destruction of any samples taken, and the investigator must document this in the site study records.

The reason for discontinuation of study treatment and/or withdrawal from the study must be recorded in the eCRF.

Refer to the Time and Events Table (Section 7.1) for the assessments to complete in the event of discontinuation of study medication and early withdrawal.

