5.6.1. Criteria for Permanent Discontinuation from Study Medication and Early Withdrawal

Subjects must **permanently discontinue study medication** for the following reasons:

- Meeting Hgb stopping criteria (Section 5.6.2).
- Receiving blood transfusions.
- Receiving kidney transplant.
- Subject becomes pregnant or intends to become pregnant during the study.
- Active GI bleeding.
- Diagnosis of cancer, with the exception of squamous cell and basal cell carcinoma.
- Liver chemistry abnormalities exceeding the threshold criteria (Section 5.6.4).
- Missing 2 consecutive dialysis sessions.
- Need for chronic (more than 14 days) use of prohibited medication (Section 6.9.2).

The subject should attend the clinic as soon as possible to complete the Early Withdrawal assessments and return for a Follow-up visit as described in Section 7.1, Time and Events.

The reason for discontinuation of study medication and date of last dose will be recorded in the eCRF.

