2.2. Study Objective(s) and Endpoint(s)

Objectives	Endpoints
Primary Objectives	Primary Endpoints

 Characterize the dose-response relationship between GSK1278863 administered three-times weekly and Hgb at Day 29 	
 Hgb change from baseline at Day 29
Secondary Objectives	Secondary Endpoints

 Characterize the pharmacodynamic (PD) effect of GSK1278863 dose regimens on EPO, vascular endothelial growth factor (VEGF), hepcidin and red blood cells 	
 Maximum observed change from baseline in EPO Maximum observed % change from baseline in VEGF Change from baseline in hepcidin at Day 29 Change from baseline in hematocrit, red blood cell (RBC) count, reticulocyte count and reticulocyte Hgb (CHr) at Day 29

 Characterize the steady-state PK of GSK1278863 and major metabolites 	
 Descriptive PK summaries of GSK1278863 and major metabolites

 Assess the safety and tolerability of GSK1278863 with three-times weekly administration for 29 days 	
 Incidence and severity of AEs and SAEs Reasons for discontinuation of investigational product Discontinuation for safety-related reasons, e.g., pre-specified stopping criteria or AE Absolute values and changes from baseline over time in laboratory parameters, ECGs and vital signs.
Exploratory Objectives	Exploratory Endpoints

 Evaluate exposure-response relationships between GSK1278863 and PD endpoints 	
 Further models (as appropriate) to describe the GSK1278863 exposure (PK or dose)-response relationship with PD endpoints

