33.	Safety	Listing 8.13	Patient Profile Listing of Cerebrovascular Events/Stroke/Transient Ischemic Attack	
34.	Safety	Listing 8.14	Patient Profile Listing of Deep Venous Thrombosis /Pulmonary Embolism	

ICH : Listings				
No.	Population	IDSL / TST ID / Example Shell	Title	Programming Notes
35.	Safety	Listing 8.15	Patient Profile Listing of Myocardial Infarction/Unstable Angina	
36.	Safety	Listing 8.16	Patient Profile Listing of Peripheral Arterial Thrombosis Embolism	
37.	Safety	Listing 8.17	Patient Profile Listing of Pulmonary Hypertension	
38.	Safety	Listing 8.18	Patient Profile Listing of Revascularisation	
39.	Safety	Listing 8.19	Patient Profile Listing of Valvulopathy	
Laboratory				
40.	Safety	LB5	Listing of Chemistry Data for Subjects with Abnormalities of Potential Clinical Importance	
41.	Safety	LB5	Listing of Hematology Data for Subjects with Abnormalities of Potential Clinical Importance	
ECGs				
42.	Safety	CP_EG3	Listing of All ECG Values for Subjects with Any Value of Potential Clinical Importance	See Section 11.8.3 for ECG value of potential clinical importance: Increase from baseline QTc > 60 msec
43.	Safety	CP_EG5	Listing of All ECG Findings for Subjects with an Abnormal Finding	
Vital Signs				
44.	Safety	CP_VS4	Listing of All Vital Signs for Subjects with any Value of Potential Clinical Importance	
Hepatobiliary (Liver)				
45.	Safety	Example LIVER5	Listing of Liver Event Results and Time of Events Relative to Treatment	

ICH : Listings				
No.	Population	IDSL / TST ID / Example Shell	Title	Programming Notes
46.	Safety	MH2	Listing of Past and Current Liver Disease Medical Conditions	Data from Liver Form: 1. Medical Conditions at Onset of Liver Event. 2. Other Medical Conditions. 3. Other Liver Disease Conditions - Liver Event.
47.	Safety	L8.43 SU2	Listing of Alcohol Intake at Time of Liver Event	
48.	Safety	Listing 8.44	Listing of Laboratory Data from Liver Event Follow-Up	
Pharmacokinetics				
49.	Pharmacokinetic	Listing 14.01	Listing of GSK1278863 and Metabolites Pharmacokinetic Plasma Concentration-Time Data	
50.	Pharmacokinetic	PK Parameter Listing	Daprodustat Plasma Pharmacokinetic Parameters for Each Treatment Group	

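### ECG and iron results required at Early Withdrawal are left out of every by-visit table when taken by Study Day 22, and some of these ECGs reach no planned display

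*SAP*

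**What the plan says.** Protocol 5.6.1 tells subjects who stop study medication what to do next: "The subject should attend the clinic as soon as possible to complete the Early Withdrawal assessments". Protocol 5.6 refers to the Time and Events table "for the assessments to complete in the event of discontinuation of study medication and early withdrawal". In that table, repeated in SAP 11.2.1, the ECG row is marked at Week -4, Day 29 and Early Withdrawal. The row "Ferritin, transferrin, total iron, UIBC" is marked at Week -4, Day 1, Day 29, Early Withdrawal and Follow-up. Neither row is marked at Day 15.

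Under SAP 11.3.1, "unscheduled and early withdrawal (EW) data measurements will be assigned to one of the protocol specified visits using the following algorithm". SAP Table 10 then sends Study Days 2 to 22 to Day 15 and Days 23 to 36 to Day 29. For parameters not scheduled at the assigned visit the section says: "However, if a value is slotted to a visit unscheduled for a parameter, it will not be summarized but will be included in data listings". The following sentence makes an exception. It begins "Assessments at unscheduled visits will be included for" and goes on to name any-time on-treatment and any-time post-treatment summaries. SAP 11.5.3 counts the Early Withdrawal visit as an unscheduled visit.

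SAP 2.2 lists as a secondary safety endpoint: "Absolute values and changes from baseline over time in laboratory parameters, ECGs and vital signs". Protocol 9.4.3.3 says that all ECG measures will go into a subject listing, and that ECG data will not be summarized by treatment group because they are read locally.

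**The concern.** The protocol orders an ECG and an iron panel at Early Withdrawal because the subject is about to leave. The windowing rule then moves those results to a visit at which they were never scheduled, and for that reason removes them from the tables. Nothing in the SAP suggests this was intended: the same section expressly slots and summarizes Early Withdrawal EPO, hepcidin and VEGF.

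For iron the loss is from the by-visit tables. For ECG it goes further. The rule relies on listings as the fallback, but the SAP plans no complete ECG listing, so some required ECGs would not be shown at all. ECG change over time is a stated secondary safety endpoint. Early withdrawals are also unlikely to be a random subset, since one route out is the hemoglobin-rise stopping criterion in Protocol 5.6.2.

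**Working it through.** **1. Slotting crossed with the schedule.** Table 10 was applied to each of Study Days 2 to 36.

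| Parameter | Scheduled at Day 15? | Early Withdrawal value, Days 2-22 | Early Withdrawal value, Days 23-36 |
|---|---|---|---|
| ECG | No | Not summarized by visit | Slotted to Day 29 |
| Ferritin, transferrin, total iron, UIBC (and TSAT, TIBC) | No | Not summarized by visit | Slotted to Day 29, shown only if on-treatment |
| Chemistry, hematology | Yes | Kept | Kept |
| Hepcidin | Yes | Kept | Kept |

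Only ECG and iron are lost. SAP 11.4.2.1 ends the on-treatment period one day after the last dose, and the Day 29 iron rows are on-treatment only. An iron sample drawn later than that is left out of the Day 29 row even when its slot is Day 29.

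**2. Where the affected values can still appear (SAP Appendix 14).**
- ECG tables: 3.30 and 3.31 are both by visit, and no any-time ECG table is planned.
- ECG listings: Listing 42 covers subjects with a QTc rise above 60 msec. Listing 43 is the "Listing of All ECG Findings for Subjects with an Abnormal Finding". Listings 51 to 81 contain no other ECG listing. A subject who meets neither condition is in neither listing.
- Iron tables: 2.33 to 2.44 (twelve) are all by visit.
- Iron listings: Listing 15 holds all six parameters for ITT subjects.
- Any-time tables 3.26 and 3.27: SAP 11.8.1 gives limits of potential clinical importance for ferritin and TSAT, and 8.2.2.2 plans these tables from the Section 11.8 limits. But 8.2.2.2 also names both as efficacy parameters that are not reported again among the laboratory evaluations. Whether they enter is unresolved.
- Follow-up iron samples are not slotted and can still enter the Day 43 row.

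**3. Scale.** Protocol 9.2 assumes at most 15% dropout: 0.15 × 90 = 13.5. Its 75 completers imply 90 − 75 = 15. Days 2 to 22 are 21 days. The documents give no timing of withdrawals, so an even spread is assumed.
- Over Days 2-28: 21/27 = 0.778, giving 13.5 × 0.778 = 10.5 to 15 × 0.778 = 11.7.
- Over Days 2-36: 21/35 = 0.60, giving 13.5 × 0.60 = 8.1 to 15 × 0.60 = 9.0.

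That is about 8 to 12 subjects.

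**4. Dose gradient, as an illustration.** Protocol 9.2.1 gives E0 = −0.666, Emax = 5.258, ED50 = 78 and SD = 1. SAP 11.7.2.1 treats the response as linear in time. A hemoglobin reading error e of 0.3 to 0.5 g/dL, contained in that SD, is assumed.
- Day 29 mean = E0 + (Emax − E0)/(1 + ED50/dose). At 30 mg: −0.666 + 5.924/3.6 = 0.980. The Day 15 mean is half of this, 0.490.
- Day 15 variance = (1 − 2e²)/4 + 2e². With e = 0.3 the SD is √0.385 = 0.620; with e = 0.5 it is √0.625 = 0.791.
- Share with a rise of at least 1.0 = 1 − Φ((1 − 0.490)/SD) = 20.5% to 25.9%.

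The same steps give 16.1% to 21.9% at 25 mg and 1.6% to 4.6% on placebo. With the protocol's other ED50 (37.28), the 30 mg share is about 49%. The share rises with dose in both cases, but its size moves with e and ED50.

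**The case against.** The strongest reply has five parts.

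- **Iron data are not lost.** This stands. All iron values remain in Listing 15, and ferritin and TSAT may be counted in Tables 3.26 and 3.27. A reader might infer that these results vanish from every iron table, and the any-time exception does not support that.
- **The ECG tables are additional.** The protocol did not plan ECG summaries by treatment group, so a gap in Tables 3.30 and 3.31 weighs less. This stands for the tables. It also makes the listing matter more, because a full listing was the protocol's only planned ECG display. SAP Table 1 does not record its removal.
- **The missing ECG listing is a separate mismatch that affects all subjects.** True, but completers' ECGs still enter the Day 29 rows. For withdrawals by Day 22 the two gaps combine and leave nothing.
- **The rule does not cause the selection.** This stands. A reader might infer that the slotting rule biases the tables toward slower responders. Any Day 29 observed-case row has that selection after dropout, and keeping a value from about Day 15 out of it is right.
- **The affected values may not be on-treatment.** This stands in part. The visit is to happen as soon as possible after stopping, not necessarily within one day of the last dose, so the treatment state must be marked for each value.

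**Conclusion.** The point holds for Early Withdrawal visits up to Study Day 22. ECG results from those visits enter no table, and iron results enter no by-visit table. An ECG from a subject with no QTc rise above 60 msec and no abnormal finding enters no display at all, contrary to Protocol 9.4.3.3.

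The size is roughly 8 to 12 of 90 subjects, given the planned maximum dropout and an even spread of withdrawals. The loss is probably larger at high dose because of the hemoglobin-rise stop at Day 15. A reader might infer that one fifth to one quarter of the 30 mg arm is lost. The documents do not establish this: the figure rests on an assumed reading error and on one of the protocol's two ED50 values, and it presumes that every subject who meets the criterion has the Early Withdrawal assessments by Day 22.

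The primary hemoglobin analysis is not touched, and the affected summaries are descriptive.

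**What to change.** 1. Add the full by-subject ECG listing that Protocol 9.4.3.3 promises.
2. In SAP 11.3.1, except parameters whose only scheduled on-treatment visit is Day 29: ECG, ferritin, transferrin, TSAT, total iron, UIBC and TIBC. Show their Early Withdrawal values in a separate row labelled Early Withdrawal in Tables 2.33 to 2.44, 3.30 and 3.31. Mark values taken more than one day after the last dose as post-treatment, and keep them out of the Day 29 row.
3. Reconcile SAP 8.2.2.2 with 11.8.1 by stating whether ferritin and TSAT enter Tables 3.26 and 3.27.

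The cost is one exception and one clarification in the SAP, one row in fourteen tables, and one listing. No new data are needed. The row will be small and will mix treatment durations, and its label should say so.

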11.3.2. Multiple Assessments

For assessments on or after Day 1, if after window assignment there are multiple valid assessments of a parameter from the central lab within the same window (nominal and slotted visit data), then the scheduled assessment at a nominal visit takes precedence over any unscheduled assessments and will be reported for summary statistics/analyses. If the scheduled assessment is missing for the target visit within the same window, then the last on-treatment value in the window will be reported for on-treatment summary statistics/analyses, and the last post-treatment value in the window will be reported for post-treatment summary statistics/analyses.

For assessments during the screening period prior to Day1, if after window assignment there are multiple valid assessments of a parameter from the central lab within the same window (nominal and slotted visit data), then the last/most recent values will be reported for summary statistics/analyses.

For the primary endpoint, Hemoglobin (Hgb), if the scheduled Hgb concentration measurement during the study (including screening, treatment, and follow-up period) from the central lab is missing and a corresponding valid HemoCue Hgb concentration measurement is available, then the HemoCue Hgb concentration measurement takes precedence over unscheduled Hgb concentration measurements within the same window and will be used for all summaries and analyses.

ECG values and vital signs measured at the local sites will be slotted and selected following the same algorithm applied to the central lab assessments described above and will be reported for summary statistics/analyses, unless otherwise specified.

All assessments, including local lab assessments, will still appear in the associated listings.

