
Model Results Presentation
 
 As described above with Posterior Estimates, model parameters estimated from the Bayesian Emax model will be summarized through means, SD, median, MCSE/SD and equal-sided 95% credibility intervals. Median and 95% credibility intervals from Bayesian analyses and the model estimates and 95% CIs from frequentist analysis will be presented for MED, TD, and selected doses corresponding to the change of -0.25, 0.25, 0.5, 0.75 and 1 g/dL in Hgb from baseline. The Hgb dose response curve will be plotted as a line through the medians (of the predicted values of Hgb change from baseline on day 29 at a series of doses) and 95% credibility bands, and overlaid on a scatter plot of the observed data. A posterior probability distribution of predicted Hgb (g/dL) change over 29 days for each treatment group will be generated. A predictive posterior probability distribution of Hgb (g/dL) change over 29 days anticipated for a future subject, for each treatment group will be plotted. Density plots for each Emax parameter showing the prior and posterior distribution for the primary analysis overlaid with sensitivity priors analyses will be generated. A predictive posterior probability plot over the dose range to describe the probability that dose will maintain Hgb within the range of [-0.5, 0.5] g/dL after 29 days for a future subject will be generated. Dose ratios estimated by different approaches will be tabulated.

Additional Results Presentation
 
Listing of Hgb (and HemoCue Hgb data), Hgb change from baseline and Hgb derived parameters will be provided.

Analysis Datasets
 
 Unless otherwise specified, efficacy inference will be based on the ITT population using an observed case dataset, comprising of all non-missing data collected up to discontinuation of study drug and withdrawal from the trial. For dose response analysis based on ITT population, the analysis dataset comprises (1) all observed non-missing Hgb data collected up to Day 29; and (2) imputed Hgb value at Day 29 for subjects who have a Day 15 Hgb measurement but a missing Day 29 Hgb measurement.

Sensitivity and Supportive Statistical Analyses

To assess the robustness of the primary efficacy conclusions the dose-response analysis will be repeated using the sensitivity approaches described below.

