11.5.3. Reporting Process & Standards

Reporting Process	
Software	

 The currently supported versions of SAS software, version 9.3. or higher will be used for all analyses unless otherwise specified. Additionally, R version 3.1.1 or higher may be used, if necessary, for analysis and the production of graphics. 	
Reporting Area	
HARP Server	: UK1SALX00175
HARP Area	: /arenv/arprod/gsk1278863/mid204836/final/
QC Spreadsheet	: /arenv/arprod/gsk1278863/mid204836/final/qc/
Analysis Datasets	

 Analysis datasets will be created according to CDISC standards (SDTM IG Version 3.1.3 & ADaM IG Version 1.1). 	
Generation of RTF Files	

 RTF files will be generated. 	
Reporting Standards	
General	

 The current GSK Integrated Data Standards Library (IDSL) will be applied for reporting, unless otherwise stated: 
 4.03 to 4.23: General Principles 5.01 to 5.08: Principles Related to Data Listings 6.01 to 6.11: Principles Related to Summary Tables 7.01 to 7.13: Principles Related to Graphics 	
Formats	

 GSK IDSL Statistical Principles (5.03 & 6.06.3) for decimal places (DP's) will be adopted for reporting of data based on the raw data collected. Numeric data will be reported at the precision collected on the eCRF. The reported precision from non eCRF sources will follow the IDSL statistical principles but may be adjusted to a clinically interpretable number of DP's. 	
Planned and Actual Time	

 Reporting for tables, figures and formal statistical analyses : 
 Planned time relative to dosing will be used in figures, summaries, statistical analyses and calculation of any derived parameters, unless otherwise stated. The impact of any major deviation from the planned assessment times and/or scheduled visit days on the analyses and interpretation of the results will be assessed as appropriate. Reporting for Data Listings: 
 Planned and actual time relative to study drug dosing will be shown in listings (Refer to IDSL Statistical Principle 5.05.1). Unscheduled or unplanned readings will be presented within the subject's listings. 	
Unscheduled Visits	

 Unscheduled visits (including early withdrawal visit) will be included in summary tables after 	

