11.7.2.1. Handling of Missing Hgb and Other Data

Element	Reporting Detail
Hgb	
 • The Hgb concentration analyzed by Quest Diagnostics is referred to as Hgb throughout this document. These data will be summarized and analyzed. If the Hgb concentration measurement is missing and a corresponding valid HemoCue Hgb concentration measurement is available, the HemoCue Hgb concentration measurement will be used for all summaries and analyses. • The dose response dataset will be based on the ITT population using an observed case dataset, comprising all non-missing data collected up to Day 29. For subjects who have a Day 15 Hgb measurement but a missing Day 29 Hgb measurement, a change from baseline at Day 29 value will be imputed using $2 * (\text{Day 15 Hgb} - \text{Baseline Hgb})$. The assumption is deemed appropriate based on phase 2a data indicating linear response over time. Any subject who prematurely

Element	Reporting Detail
	
discontinues dosing prior to Day 15 will be non-evaluable for the dose-response analysis. In general, the imputed data for the dose response analysis will not be used in summaries and figures, except for those generated specifically for dose response results. However, for descriptive summaries of Hgb over time, raw Day 29 Hgb will be summarised as well as Day 29 Hgb including imputations. The number of imputed Day 29 Hgb values will be summarized by treatment group.
 
• All other efficacy inference will be based on the ITT population using an observed case dataset.
Other Data	
• For laboratory data no imputation for missing data or premature discontinuation will be performed and the observed values will be used. The same approach applies to other assessments such as vital signs and electrocardiograms (ECGs) examination data.

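### When Day 29 Hgb is missing, the fixed doubling of the Day 15 change ignores later on-treatment readings and takes no account of the reading's actual study day; few subjects are affected

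*SAP*

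**What the plan says.** **Slotting.** SAP 11.3.1 states that "unscheduled and early withdrawal (EW) data measurements will be assigned to one of the protocol specified visits". Its Table 10 sends Study Days 2 to 22 to Day 15 and Days 23 to 36 to Day 29. SAP 11.5.3 treats early withdrawal as one kind of unscheduled visit: "Unscheduled visits (including early withdrawal visit) will be included in summary tables after" slotting.

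**Precedence within a window (SAP 11.3.2).** Three tiers apply to Hgb:
- If a scheduled central-laboratory value exists, "then the scheduled assessment at a nominal visit takes precedence over any unscheduled assessments and will be reported for summary statistics/analyses". There is no condition on which reading is later.
- If that value is missing but a matching HemoCue value exists, "then the HemoCue Hgb concentration measurement takes precedence over unscheduled Hgb concentration measurements within the same window".
- Failing both: "If the scheduled assessment is missing for the target visit within the same window, then the last on-treatment value in the window will be reported".

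**Imputation.** SAP 7.1.2 adds to the dose-response dataset an "imputed Hgb value at Day 29 for subjects who have a Day 15 Hgb measurement but a missing Day 29 Hgb measurement". SAP 11.7.2.1 gives the formula, 2 × (Day 15 Hgb − baseline Hgb), and its justification: "The assumption is deemed appropriate based on phase 2a data indicating linear response over time". The programming notes for efficacy Table 2.5 (SAP 11.14.6) require only that the Day 15 value be on-treatment, which SAP 11.4.2.1 defines for laboratory data as no later than one day after the treatment stop date. Protocol 9.3.2 also bases the imputation on Day 1 and Day 15 data.

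**The concern.** The window and precedence rules were written for by-visit tables, where preferring the scheduled visit is sensible. The primary dose-response dataset inherits them, and there they decide which reading is extrapolated to Day 29.

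Two consequences follow for a subject without a usable Day 29 value:

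1. **A scheduled Day 15 value exists.** A later on-treatment reading from Days 16 to 22, closer to the endpoint, has no stated route into the imputation. The Day 15 change is doubled instead.
2. **No scheduled Day 15 value exists, by central laboratory or HemoCue.** The last on-treatment reading in the window stands in as Day 15 and its change is doubled, although a factor of 2 is right only for a reading taken on Day 15.

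Imputed changes enter the Emax and linear fits alongside observed ones, under a constant error variance. Those fits yield the target dose (TD), the minimally effective dose (MED) and the dose ratio. Neither the completer analysis nor the repeated-measures model uses the later reading: the first drops these subjects, and the second takes one value each for Day 15 and Day 29.

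SAP 11.3.1 does say that unscheduled assessments feed algorithms drawing on additional data, but it does not say whether the imputation is one of them.

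**Working it through.** **The plan's own multiplier.** If change is linear in time from Day 1, a reading on study day d is projected to Day 29 by f(d) = (29 − 1)/(d − 1) = 28/(d − 1). At d = 15 this is 28/14 = 2, the SAP's figure. The factor is therefore correct for a reading on Day 15.

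**Case 1: precision.** Let each reading have error SD v, independent between readings. Baseline is the mean of two readings (SAP 11.5.2.1), so its error variance is v²/2. The imputed change then has RMSE = f × √(v² + v²/2) = f × √1.5 × v. The documents give no v; 0.5 g/dL is assumed, with a range of 0.3 to 0.6.

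| Reading used | f | RMSE, v = 0.5 | RMSE, v = 0.3 to 0.6 | Reduction against Day 15 |
|---|---|---|---|---|
| Day 15 | 2.00 | 1.22 | 0.73 to 1.47 | – |
| Day 20 | 1.47 | 0.90 | 0.54 to 1.08 | 26% |
| Day 22 | 1.33 | 0.82 | 0.49 to 0.98 | 33% |

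The percentage reductions do not depend on v.

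Invented pairs of changes show the consequence for one subject (g/dL):

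| Day 15 | Day 22 | SAP imputes | From Day 22, × 28/21 |
|---|---|---|---|
| +0.3 | +0.45 (exactly linear) | +0.6 | +0.6 |
| +0.3 | +0.9 | +0.6 | +1.2 |
| +0.6 | +0.3 | +1.2 | +0.4 |

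Under exact linearity the two agree, so the expected loss is precision and not bias.

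**Case 2: wrong projection.** Doubling the change on day d projects to day 1 + 2(d − 1). For d = 22 that is Day 43, and the over-extrapolation is 2 × 21/28 = 1.5-fold. A Day 22 change of +0.45 enters as +0.9 where linearity gives +0.6.

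**How many subjects.** Protocol 9.2 allows at most 15% dropout of about 90, i.e. 13.5; the gap between 90 randomized and 75 evaluable is 15. If stopping were spread evenly over Days 2 to 28 (assumed), the share in Days 16 to 22 is 7/27, giving 3.5 to 3.9 subjects. These are stoppers. To be affected, a subject also needs a reading no later than stop date + 1. Doses are taken on dialysis days, so a three-times-weekly patient first seen at the next session, without a dose, is at least two days past the last dose and already post-treatment. A count of 0 to 2 is a judgement from these filters and not a calculated figure.

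**Effect on the estimates.** Take one affected subject in an arm of 15, off by 0.3 to 0.8 g/dL (0.6 and 0.8 are the gaps in the second and third rows above):
- Arm mean: 0.3/15 to 0.8/15 = 0.02 to 0.05 g/dL. With the protocol's SD of 1 g/dL, the standard error of an arm mean is 1/√15 = 0.26.
- Linear slope: for 15 subjects at each of 0, 10, 15, 25 and 30 mg the mean dose is 16 and Sxx = 15 × (256 + 36 + 1 + 81 + 196) = 8550. If the subject is in the 30 mg arm, the slope moves by 14 × 0.3/8550 to 14 × 0.8/8550 = 0.0005 to 0.0013. That is 1.0% to 2.6% of the planned 0.05 and well inside the 0.018 to 0.020 half-width that protocol Table 5 gives for that slope at SDx 11.0 and 10.0 with SDy 1.0.

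**The case against.** The strongest defence is that the rule is coherent, pre-specified and agrees with the protocol, and that it touches almost nobody. Most of this stands.

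- **Size.** A reader might infer that 3 or 4 of 90 subjects carry a poor value. The documents do not support this: that figure counts assumed stoppers at the maximum dropout rate, before the stop date + 1 filter.
- **Reversal after a large rise.** A reader might picture a subject at +1.0 g/dL on Day 15 who has fallen back by Day 22. Under protocol 5.6.2 a confirmed rise of at least 1.0 g/dL over two weeks leads to permanent discontinuation, so that Day 22 reading would usually be post-treatment and unusable under either rule. It is not strictly impossible, because the criterion uses HemoCue over two weeks and the endpoint uses central-laboratory change from an averaged baseline.
- **Safeguards.** The completer analysis leaves these subjects out, imputed counts are tabulated by arm, Day 29 is summarized with and without imputation, and the later readings stay in the listings.
- **Newer is not always better.** An early-withdrawal reading may reflect the event that led to stopping. Protocol section 7 keeps the Day 15 and Day 29 visits off the first weekly dialysis session for three-times-weekly patients, and the per-protocol check on session timing (SAP 11.1.2) covers only those two visits. This has some force. But the SAP already accepts on-treatment unscheduled and early-withdrawal readings in the Day 29 window and, when the scheduled value is missing, in the Day 15 window.

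The defence does not answer the second case, where a factor that is right for Day 15 is applied to any day in the window.

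**Conclusion.** The point holds as a low-priority improvement. The rules leave a later on-treatment reading from Days 16 to 22 unused whenever a scheduled Day 15 value exists, and double a stand-in reading without regard to its day when none exists. On the SAP's linearity assumption the first costs precision: RMSE could be 26% to 33% lower from a Day 20 or Day 22 reading if errors are equal and independent across scheduled and unscheduled samples. The second is an extrapolation error, 1.5-fold at Day 22.

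Probably 0 to 2 subjects are affected, and the effect on TD, MED and the dose ratio is small. A reader might go further and infer that the multiplier is wrong in general or that the primary result is biased. Neither is supported: the factor of 2 fits a Day 15 reading, and under linearity the first case introduces no bias. The Hgb reading itself is not doubled; its change from baseline is.

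**What to change.** In SAP 11.7.2.1, for the dose-response dataset only, state that when no on-treatment Hgb falls in the Day 29 window, the last on-treatment Hgb from the Day 15 visit through Day 22 (scheduled, unscheduled or early withdrawal) is used, and the change is imputed as 28/(study day − 1) × (Hgb − baseline). For a subject with no Day 15 visit, give the start of that range as a study day; the ±2-day visit window makes Day 13 the natural choice. Keep scheduled-first precedence for the by-visit tables. Add a row to SAP Table 1, because protocol 9.3.2 names Day 1 and Day 15 data as the basis.

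The two parts belong together: using the later reading while keeping the factor of 2 would carry the second case's error into the first.

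**Cost.** One sentence, one derivation line and one table row.

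**Downsides.**
- The rule rests on the same linearity assumption as the present one.
- The multiplier also changes for imputed subjects whose scheduled Day 15 visit was off-day: 28/12 = 2.33 at Day 13, down to 28/16 = 1.75 at Day 17.
- Unscheduled readings are not checked for first-dialysis-session timing.
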